10.8.5. Version History

Table 22: Primary Reason for Each Version

Version	Primary Reason for Version
4.0	To revise study assessments/sample collection and incorporate COVID-19 vaccine approvals
3.2	Administrative amendment to update the Sponsor contact information and to correct minor errors in Version 3.1
3.1	Administrative amendment to correct minor errors in Version 3.0
3.0	To incorporate Version 2.0 country-specific changes into a global amendment
2.0 (3 country-specific amendments)	To address country-specific requests from Czech Republic/Italian, German, and United Kingdom regulatory authorities after their review of global Version 1.0. There was no global Version 2.0.
1.0	Original version

**REVISION HISTORY**

Version No.	Effective Date	Summary of Change(s)
0.1	29 May 2019	New document
0.2	12 August 2019	Incorporate internal reviewer's comments
1.0	22 August 2019	Incorporate final comments, finalize for signatures
1.1	26 August 2021	Updates per protocol v4.0, document sponsor change from Verastem to Secura Bio., add summaries for COVID-19 related protocol deviations
2.0	31 August 2021	Incorporate all changes, finalize for signatures.
2.1	19 May 2023	Updates per dry run comments: Add Kaplan Meier and Forest plots for efficacy analyses Add AESI for COVID-19 Change TEAE summaries currently by SOC, HLGT, and PT to by SOC and PT
3.0	09 August 2023	Incorporate final comments, finalize for signatures.

## LIST OF ABBREVIATIONS

Abbreviation / Acronym	Definition / Expansion
AE	Adverse event
ALT	Alanine aminotransferase
AST	Aspartate aminotransferase
AT	All-treated
ATC	Anatomical Therapeutic Chemical
BID	Twice daily
BLQ	Below the limit of quantification
BMI	Body mass index
BP	Blood pressure
CI	Confidence interval
CLL	Chronic lymphocytic leukemia
CR	Complete response
CS	Clinically significant
CTCAE	Common Terminology Criteria for Adverse Events
ctDNA	circulating tumor DNA
DNA	Deoxyribonucleic acid
DOR	Duration of response
ECG	Electrocardiograms
ECHO	Echocardiogram
ECOG	Eastern Cooperative Oncology Group
eCRF	Electronic case report form
EQ-5D-3L	EuroQoL 5-dimensions 3-level
FL	Follicular lymphoma
HLGT	High-level group term
ICF	Informed consent form
iNHL	Indolent Non-Hodgkin's Lymphoma
IWG	International Working Group
KM	Kaplan-Meier

Abbreviation / Acronym	Definition / Expansion
LLQ	Lower limit of quantitation
LNRR	Lymph node response rate
MedDRA	Medical Dictionary for Regulatory Activities
mITT	Modified intent-to-treat
MUGA	Multigated acquisition
MZL	Marginal zone lymphoma
NCI	National Cancer Institute
NCS	Not clinically significant
ORR	Overall response rate
OS	Overall survival
PD	Progressive disease
PE	Physical examination
PFS	Progression-free survival
PK	Pharmacokinetics
PP	Per-protocol
PR	Partial response
PT	Preferred Term
QoL	Quality of Life
RBC	Red blood cell
RNA	ribonucleic acid
R/R	Relapsed or refractory
SAE	Serious adverse event
SAP	Statistical analysis plan
SD	Standard deviation
SI	International System of Units
SLL	Small lymphocytic lymphoma
SoA	Schedule of assessments
SOC	System organ class
TEAE	Treatment-emergent adverse event
TTF	Time to treatment failure

Abbreviation / Acronym	Definition / Expansion
TTFR	Time to the first response
VAS	Visual Analog Scale
WHODrug	World Health Organization - Drug Dictionary

## 1 INTRODUCTION

Dosing with duvelisib 25 mg twice daily (BID) has been shown to be efficacious in multiple Phase 1-3 studies including subjects with indolent non-Hodgkin lymphoma (iNHL). The efficacy, safety and tolerability of this dose supported the U.S. approval of duvelisib for the treatment of adult subjects with relapsed or refractory (R/R) chronic lymphocytic leukemia (CLL)/small lymphocytic lymphoma (SLL) after at least 2 prior therapies and accelerated approval in adult subjects with R/R follicular lymphoma (FL) after at least 2 prior systemic therapies. The current study will evaluate whether efficacy can be achieved and maintained, with acceptable or improved safety and tolerability, by inclusion of pre-specified 2-week drug holidays in 2 different 25 mg BID schedules in subjects with R/R iNHL.

This statistical analysis plan (SAP) provides a detailed description of the statistical methods and analyses to be carried out in support for study VS-0145-229.

The following will be collected but not entered into the clinical study database:

- Pharmacokinetic data (PRA Health Sciences)
- Pharmacodynamic data (Primity Bio)
- Exploratory biomarkers (Covance)

The analyses described in this SAP are based upon the following study documents:

- Study Protocol, Version 1.0 (April 4, 2019)
- Study Protocol, Version 4.0 (May 19, 2021)
- electronic Case Report Form (eCRF), Version 1.0 (August, 21, 2019)
- electronic Case Report Form (eCRF), Version 9.0 (23 Sep 2022)

## 2 STUDY OBJECTIVES

### 2.1 Primary Objective(s)

Evaluate the efficacy of duvelisib administered with prescribed drug holidays in subjects with iNHL.

### 2.2 Secondary Objective(s)

- Evaluate supportive efficacy measures of duvelisib administered with prescribed drug holidays in subjects with iNHL.
- Evaluate the safety and tolerability of duvelisib administered with prescribed drug holidays in subjects with iNHL.
- Characterize the pharmacokinetics (PK) of duvelisib metabolite(s) and duvelisib when duvelisib is administered with prescribed drug holidays in subjects with iNHL.

### 2.3 Exploratory Objective(s)

- Evaluate Quality of Life (QoL) in subjects treated with duvelisib with prescribed drug holidays.
- Evaluate potential biomarkers of clinical efficacy and/or safety of duvelisib administered with prescribed drug holidays in subjects with iNHL.

## 3 INVESTIGATIONAL PLAN

[figure not shown]
### 3.1 Overall Study Design and Plan

This is a Phase 2, randomized, open-label, multicenter, international 2-arm study designed to evaluate the efficacy and safety of alternative dosing schedules of duvelisib treatment in subjects with R/R iNHL who have received at least 1 prior systemic therapy.

Subjects will be stratified by the number of prior therapies (1 or  $> 1$ ), bulky disease status (longest diameter of baseline lesion  $< 5$  cm or  $\geq 5$  cm) and time since last recurrence ( $\geq 24$  months or  $< 24$  months).

Subjects will be randomized to Arm 1 or Arm 2 in a 1:1 fashion.

- Arm 1: duvelisib 25 mg BID for one 10-week cycle followed by 25 mg BID on Weeks 3 and 4 of each subsequent 4-week cycles until disease progression, unacceptable toxicity, or withdrawal.
- Arm 2: duvelisib 25 mg BID on Weeks 1, 2, 5, 6, 9 and 10 of one 10-week cycle, then on Weeks 3 and 4 of each subsequent 4-week cycles until disease progression, unacceptable toxicity, or withdrawal (Figure 1).

**Figure 1: Treatment Scheme**

Solid sections: duvelisib 25 mg BID; hashed sections: drug holiday. Subjects will be randomized 1:1 to Arms 1 and 2. Subjects will be assessed for disease response on Day 1 of Cycles 2, 4, 6, 9, 13, 17 and every fourth cycle thereafter until disease progression, unacceptable toxicity or withdrawal.

Abbreviations: BID: twice daily.

The study has a 2-stage design. For each arm: in the first stage, 15 subjects will be enrolled. Responses will be assessed by the Investigator according to the 2007 revised IWG criteria (Cheson 2007) (primary endpoint) and the 2014 Lugano criteria (Cheson 2014). The evaluation of the first stage will take place after the enrolled subjects have been followed for a minimum of 3 cycles. If there are fewer than 6 responders (partial response (PR) or complete response (CR)) among the first 15 subjects per arm, consideration may be given to stopping that arm. A treatment arm may also not proceed to the second stage if the totality of the data is compelling (e.g., accumulating enough data in Stage 1 to conclude the overall response rate (ORR) exceeds 30%). Otherwise, approximately 36 additional subjects will be enrolled for a total of 51 per arm. Enrollment will be continuous between Stage 1 and Stage 2. If fewer than 22 (43%) responders (PR or CR) are observed in 51 subjects, consideration may be given to concluding that the treatment schedule does not warrant further study in this population. Each arm will be evaluated separately.

It is anticipated that study enrollment will occur over approximately 2 years. The last subject visit will occur 2 years after the last subject is randomized. If the study ends prior to all subjects discontinuing treatment, any subject continuing to receive benefit will be provided the opportunity to continue to receive duvelisib. Long-term continued treatment may be provided via an expanded access program consistent with local regulations, such as the Secura Bio NPP. Study procedures and their timing are summarized in the schedule of assessments (SoA) (Protocol Section 1.3).

### 3.2 Endpoints

#### Primary Endpoint

Overall Response Rate (ORR) according to the 2007 revised International Working Group (IWG) Criteria (Cheson 2007)

#### Secondary Endpoints

- ORR according to 2014 Lugano criteria (Cheson 2014)

*Note: with the exception of time to treatment failure, all additional secondary response endpoints listed below as well as progression-free survival (PFS), will be assessed separately using 2007 revised IWG criteria (Cheson 2007; referred to as "revised IWG criteria" for subsequent references in this document) and 2014 Lugano criteria (Cheson 2014; referred to as "Lugano criteria" for subsequent references in this document).*

- ORR, at 6, 12, 18, and 24 months after first dose of study intervention
- PFS
- Time to treatment failure (TTF)
- Duration of response (DOR)
- Overall survival (OS)
- Lymph node response rate (LNRR)
- Time to the first response (TTFR)
- Adverse events (AEs), serious AEs (SAEs), vital signs, physical examinations, and clinical laboratory values
- PK parameters for duvelisib and metabolite(s)

#### Exploratory Endpoints

- Eastern Cooperative Oncology Group (ECOG) Performance Score
- EuroQoL 5 dimensions 3-level (EQ-5D-3L) questionnaire responses
- Blood assessments of immune cell populations, chemokines, cytokines, proteins and/or circulating tumor (ctDNA)
- Assessments of protein, DNA and or RNA in fecal microbiota
- Tumor biopsy evaluation of biomarkers such as gene and copy variation, RNA expression, protein expression, and/or immune cell content

##### 3.2.1 Efficacy Variables

Assessment of disease response and progression status in all subjects will be evaluated by the Investigator using 2007 revised IWG criteria (Cheson 2007) and 2014 Lugano criteria (Cheson 2014). Response and progression will be evaluated using the following procedures, on Day 1 of Cycles 2, 4, 6, 9, 13, 17 and every fourth cycle thereafter, as shown in the SoA (Protocol Section 1.3).

- Focused physical examination (PE) (including assessment of liver and spleen and review of disease-related constitutional symptoms)
- Imaging scans of chest, abdomen, and pelvis
- Bone marrow biopsy/aspirate (as necessary to confirm CR)

These evaluations will be done until progressive disease (PD) is documented, other anticancer therapy is initiated, or death occurs. For subjects who discontinue study intervention for reasons other than radiologic disease progression, response assessments will be performed during protocol-specified long-term follow-up.

### 3.2.2 Safety Variables

- Physical examinations, including assessment of liver/spleen size, clinical assessment of tumor masses (if evaluable by PE), review of disease-related constitutional symptoms (B symptoms: symptoms of fever [i.e., temperature  $> 38^{\circ}\text{C}/100.4^{\circ}\text{F}$ ] without evidence of infection, weight loss, and drenching night sweats without evidence of infection), neurologic examination, height
- Vital signs (semi-supine systolic and diastolic blood pressure [BP] and pulse, temperature, respiratory rate)
- 12-lead electrocardiograms (ECGs): PR interval, QRS interval, RR interval, QT interval and Fridericia's correction [QTcF])
- Echocardiogram (ECHO)/multigated acquisition (MUGA) scans (may be performed as clinically indicated per Investigator's judgement)
- Clinical laboratory tests (hematology, clinical chemistry, urinalysis and immunoglobulins parameters)
- Adverse event (AE) assessments
- Concomitant medication assessments

### 3.3 Exploratory Variables

- ECOG Performance Status
- EQ-5D-3L questionnaire (Subject Self-reported Health-related QoL)
- Blood assessments of immune cell populations, chemokines, cytokines, proteins and/or circulating tumor (ctDNA)
- Assessments of protein, DNA, and or RNA in fecal microbiota
- Tumor biopsy evaluation of biomarkers such as gene and copy number variation, RNA expression, protein expression, and/or immune cell content

## 4 STATISTICAL METHODS

### 4.1 Data Quality Assurance

All tables, figures and data listings to be included in the report will be independently checked for consistency, integrity and in accordance with standard Parexel procedures.

### 4.2 General Presentation Considerations

Baseline is defined as the last available pre-treatment assessment (scheduled or unscheduled). 'Treatment Day' will be calculated relative to the date of randomization, i.e., Treatment Day = Assessment Date - First Dose Date + 1.

The following visit windows will be defined for the purposes of determination of ORR per Lugano and revised IWG criteria at 6, 12, 18 and 24 months:

Timepoint	Visit Window
Month 6	155 – 211 (183 ± 28 days) from first dose
Month 12	351 - 407 days (379 ± 28 days) from first dose
Month 18	463 – 519 days (491± 28 days) from first dose
Month 24	687 – 743 days (715 ± 28 days) from first dose

For other by-visit summaries, data will be categorized based on the scheduled visit (i.e. cycle) specified on the eCRF on which the data were collected.

Continuous data will be summarized in terms of the mean, standard deviation (SD), median, minimum, maximum and number of observations, unless otherwise stated. Continuous data that are expected to be skewed will be presented in terms of the maximum, upper quartile, median, lower quartile, minimum and number of observations. The minimum and maximum will be reported to the same number of decimal places as the raw data recorded in the database. The mean, median, lower quartile and upper quartile will be reported to one more decimal place than the raw data recorded in the database. The SD will be reported to two more decimal places than the raw data recorded in the database. In general, the maximum number of decimal places reported shall be four for any summary statistic.

Categorical data will be summarized in terms of the number of subjects providing data at the relevant time point (n), frequency counts and percentages. Any planned collapsing of categories will be detailed in the SAP text and the data displays.

Percentages will be presented to one decimal place. Percentages will not be presented for zero counts. Percentages will be calculated using n as the denominator. If sample sizes are small, the data displays will show the percentages, but any textual report will describe frequencies only.

Changes from baseline in categorical data will be summarized using shift tables where appropriate.

P-values greater than or equal to 0.001, in general, will be presented to three decimal places. P-values less than 0.001 will be presented as “<0.001”.

Confidence intervals (CIs) will be presented to one more decimal place than the raw data.

Time-to-event endpoints (PFS, DOR, OS, TTF) will be estimated using the Kaplan-Meier (KM) method. Descriptive statistics for analyses of such endpoints will include number of events, number of subjects censored, estimated 25% quartile, estimated median, estimated 75% quartile, and 95% CI for median estimate. Detailed descriptions of the time-to-event analyses to be performed for secondary endpoints are described in [Section 4.10.3](#).

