1.3. Schedule of Activities (SoA)

Table 1: Study Activities for Duvelisib Monotherapy (Cycle 1: 10 Weeks; Cycles ≥2: 4 Weeks)

Activity	Screening D-30 to D-1	Cycle 1					Cycle 2		Cycle 3+	EoT ^a	Safety F/U ^b 30d (+7) postdose		Notes
		D1	D14 (-3)	D29 (+3)	D43 (±3)	D57 (±3)	D1 (±3)	D14 (-3)					
Informed Consent	X												Potentially eligible subjects must sign an ICF prior to initiating any study specific procedures. Standard of care assessments that fulfill study eligibility requirements may be performed prior to subject signing the ICF.
Inclusion/Exclusion Criteria	X												
Randomization	X (D -7 to -1)												Subject must sign informed consent, meet inclusion/exclusion criteria, and complete all other screening activities prior to randomization.
Medical History, Demographics	X												Medical History includes histologic lymphoma diagnostic and prior treatment and response information, FLIPI-1 score
Archival Tumor Tissue	X												Tumor tissue is not required for enrollment, but should be submitted from all enrolled subjects, if available. Sample should be FFPE tissue and will be used to evaluate prognostic biomarkers.
Tumor Biopsy (optional)	X												If a transformation to a more aggressive subtype of lymphoma is suspected, a biopsy may be performed at Investigator's discretion. If this sample is collected, please see Archival Tumor Tissue instructions above.
Full Physical Examination	X	X											If performed within 7 days of C1D1, then screening results can be used for C1D1.
Focused Physical Examination			X	X	X	X	X	X	X	X			Disease-focused assessments including liver/spleen size, clinical assessment of tumor masses, and B symptoms.
Vital Signs	X	X	X	X	X	X	X	X	X	X			Vital signs measured in a semi-supine position after 5 minutes rest.
Computed Tomography (CT)	X									X			All subjects require CT or FDG-PET-CT scans. MRI may be used instead of CT scans if CT cannot

Activity	Screening D-30 to D-1	Cycle 1					Cycle 2		Cycle 3+	EoT ^a	Safety F/U ^b 30d (+7) postdose		Notes		
		D1	D14 (-3)	D29 (+3)	D43 (±3)	D57 (±3)	D1 (±3)	D14 (-3)	D1 (±3)						
Scans of the Chest, Abdomen and Pelvis		Day 1 of Cycles 2, 4, 6, 9, 13, 17, and Every 4th Cycle Thereafter (Window: Day -7 to Day 1 of Each Cycle)											be done, but the same method must be used throughout the study. A scan will be performed at the EoT if one was not performed within 30 days of the EoT Visit.		

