6.7. Dose Modification

For dose modifications and dose level recommendations refer to [Table 8](#). Duvelisib may be held up to 42 days for toxicity. Doses held for > 42 days due to treatment-related toxicity will result in permanent discontinuation from duvelisib. Any subject who requires a dose level reduction to below 15 mg BID due to treatment-related toxicities will be permanently discontinued from duvelisib treatment.

If duvelisib treatment is permanently discontinued due to an AE, subjects should be followed for disease response and survival as outlined in the SoA ([Table 1](#)).

Dosing levels for duvelisib are shown in [Table 8](#).

Table 8: Duvelisib Dosing Levels

Dose Level	Duvelisib Dosing Levels
1	25 mg BID
-1	15 mg BID
-2	Discontinue duvelisib if subject is unable to tolerate 15 mg BID

Abbreviations: BID: twice daily

Subjects who have a dose reduction due to a toxicity will not be eligible for a dose re-escalation.

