9. STATISTICAL METHODOLOGY

A detailed description of the statistical methodology for this study can be found in the Statistical Analysis Plan (SAP). Deviations from the statistical analyses outlined in this protocol will be indicated in the SAP; any further modifications will be noted in the final clinical study report.

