9.4.3. Secondary Efficacy Endpoints Analyses

- ORR according to 2014 Lugano criteria ([Cheson 2014](#))

Note: all additional secondary response endpoints will be assessed separately using 2007 revised IWG criteria ([Cheson 2007](#)) and 2014 Lugano criteria ([Cheson 2014](#))

- ORR, at 6, 12, 18, and 24 months after first dose of study intervention, defined as the proportion of subjects achieving CR or PR at each of these time points.
- PFS will be assessed using KM methods from time of first dose of study intervention to PD or death.
- TTF will be calculated as the time from first dose of study intervention until discontinuation for any reason and will be summarized using KM methods.
- DOR will be calculated for those subjects with a CR or PR from the time of first response to PD using KM methods.

- OS will be assessed using KM methods from time of first dose of study intervention to death.
- LNRR will be calculated as the proportion of subjects achieving $\geq 50\%$ decrease in the sum of the product of the diameters (SPD) of target lymph nodes.
- TTFR will be calculated for those subjects with a CR or PR from the time of first dose of study intervention to time of first CR or PR.

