#### 4.10.3 Secondary Efficacy Variables

The secondary efficacy analyses will be conducted on the mITT analysis set.

- ORR according to 2014 Lugano criteria (Cheson 2014) will be analyzed in the same fashion as the primary endpoint

*Note: with the exception of TTF, all additional secondary response endpoints (described below) as well as PFS will be assessed separately using 2007 revised IWG criteria (Cheson 2007) and 2014 Lugano criteria (Cheson 2014)*

- ORR, at 6, 12, 18, and 24 months after first dose of study intervention, defined as the proportion of subjects achieving CR or PR at each of these time points.
- PFS will be assessed using KM methods from time of first dose of study intervention to PD or death. Median PFS will be estimated, along with the 95% CI. The 6-month and 12-month PFS estimates will also be presented. See Table 1 for event and censoring definitions. Kaplan-Meier survival curves by arm will be produced.
- TTF will be calculated as the time from first dose of study intervention until discontinuation for any reason and will be summarized using KM methods. Median TTF will be estimated, along with the 95% CI. The 6-month and 12-month TTF estimates will also be presented. Subjects who are still on treatment at time of data cutoff will be censored at their last dose date. Kaplan-Meier survival curves by arm will be produced.
- DOR will be calculated for those subjects with a CR or PR from the time of first response to PD using KM methods. Median DOR will be estimated, along with the 95% CI. The 6-month and 12-month DOR estimates will also be presented. See Table 1 for event and censoring definitions. Kaplan-Meier survival curves by arm will be produced.
- OS will be assessed using KM methods from time of first dose of study intervention to death. Median OS will be estimated, along with the 95% CI. The 6-month and 12-month OS estimates will also be presented. Subjects without documented death will be censored at their last known alive date. Kaplan-Meier survival curves by arm will be produced.
- LNRR will be calculated as the proportion of subjects achieving  $\geq 50\%$  decrease in the sum of the product of the diameters of target lymph nodes. A 2-sided 95% exact CI for LNRR will also be estimated. A waterfall plot of minimum percent change in the sum of the product of the diameters by arm will be produced.

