#### 4.14 Changes in the Conduct of the Study or Planned Analysis

Additional analyses not specified in this SAP may be conducted, if necessary. In such cases, a separate analysis plan will be created to document such analyses. The SAP will be updated as necessary if the protocol is amended.

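### The SAP's Month 18 response window is the Cycle 17 scan at about 16 months, and it closes 29 days before month 18

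*SAP*

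**What the plan says.** Protocol 9.4.3 lists "ORR, at 6, 12, 18, and 24 months after first dose of study intervention" as a secondary endpoint. SAP 4.10.3 keeps those four time points, with the endpoint "defined as the proportion of subjects achieving CR or PR at each of these time points", to be assessed by the 2007 IWG and the 2014 Lugano criteria.

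SAP 4.2 turns the time points into day windows. Month 6 is days 155 to 211, Month 12 is days 351 to 407, Month 18 is "463 – 519 days (491± 28 days) from first dose", and Month 24 is days 687 to 743.

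The Schedule of Activities (Protocol 1.3, Table 1) places the scans at "Day 1 of Cycles 2, 4, 6, 9, 13, 17, and Every 4th Cycle Thereafter (Window: Day -7 to Day 1 of Each Cycle". The same table gives 10 weeks for Cycle 1 and 4 weeks for each later cycle.

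On departures from the protocol, Protocol 9 states: "Deviations from the statistical analyses outlined in this protocol will be indicated in the SAP". SAP 4.14 says that "The SAP will be updated as necessary if the protocol is amended" and provides for additional analyses, but records no change to the 18-month endpoint.

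**The concern.** The labels in the SAP 4.2 table are six months apart, but the window centres are 196, 112 and 224 days apart. The short middle step suggests that the Month 18 row is tied to a scan well before month 18.

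The study asks whether efficacy is maintained when drug holidays are built in, and response rates at fixed times bear on that question. If the window lies about two months early, a response lost between roughly 16 and 18 months would still be reported as an 18-month response. The label alone would not show this.

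**Working it through.** **Inputs.** Cycle 1 is 70 days and each later cycle 28 days (Protocol 1.3; Protocol 9.2 agrees, equating 3 cycles with 18 weeks: 10 + 4 + 4). First dose is Day 1, by the SAP 4.2 formula for treatment day. One month is 365.25/12 = 30.4375 days, the SAP 4.11.1 exposure convention.

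**Reproducing the SAP's centres.** Day 1 of Cycle k (k ≥ 2) falls on day 71 + 28 × (k − 2):

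- Cycle 6: 71 + 28 × 4 = 183
- Cycle 13: 71 + 28 × 11 = 379
- Cycle 17: 71 + 28 × 15 = 491
- Cycle 21: 71 + 28 × 19 = 603
- Cycle 25: 71 + 28 × 23 = 715

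The four SAP centres (183, 379, 491, 715) are exactly Day 1 of Cycles 6, 13, 17 and 25, and each centre ± 28 gives the printed limits.

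**Comparing each window with its label.**

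| Label | Labelled date (months × 30.4375) | Window | Centre minus labelled date | Contains labelled date? |
|---|---|---|---|---|
| Month 6 | 182.6 | 155–211 | +0.4 days | yes |
| Month 12 | 365.25 | 351–407 | +13.8 days | yes |
| Month 18 | 547.9 | 463–519 | −56.9 days | no |
| Month 24 | 730.5 | 687–743 | −15.5 days | yes |

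The Month 18 centre is at 491/30.4375 = 16.1 months. Its upper limit is at 519/30.4375 = 17.05 months, which is 547.9 − 519 = 28.9 days short of month 18. With a month of 365.5/12 days (the SAP 4.7 convention) the shortfall is 29.2 days. With calendar months (18 months = 546 to 550 days) it is 27 to 31 days.

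**Is any scheduled scan near month 18?** A window of ± 28 days around day 548 would be days 520 to 576.

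- Cycle 17 scans are due on days 484–491; Day 1 is 547.9 − 491 = 56.9 days before month 18.
- Cycle 21 scans are due on days 596–603; Day 1 is 603 − 547.9 = 55.1 days after it.
- Allowing the ± 3-day visit window as well widens these to days 481–494 and 593–606, and neither range reaches days 520–576.

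So moving the window to month 18 would leave it empty on schedule. A Cycle 21 window built in the same way (603 ± 28 = days 575–631) would also miss day 548.

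**What happens to an off-schedule scan.** Days 520 to 686 (686 − 520 + 1 = 167 days) belong to no landmark window. That stretch contains both day 548 and the Cycle 21 scan.

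**The case against.** The strongest reply is that the problem starts in the protocol. It asks for an 18-month rate but schedules no scan near month 18, so any SAP must use a scan at some other time. This SAP chose Cycle 17 and printed the day range, and its ± 28 arithmetic is correct. That much stands: the fault is in the label and choice of visit, not in the sums. But nothing in the SAP says that Month 18 means about month 16 or why Cycle 17 was preferred to Cycle 21, which is slightly nearer. The offset is also about twice the tolerance the SAP allows itself.

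Actual scan days may differ from the nominal schedule. An end-of-treatment scan may fall between cycles: "A scan will be performed at the EoT if one was not performed within 30 days of the EoT Visit". Holds may also matter: "Duvelisib may be held up to 42 days for toxicity"; the documents do not say whether cycle dates then shift. This does not rescue the row, because the window is fixed in days from first dose and would exclude a scan on day 548.

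Days outside every window are not in themselves a defect. Days 212–350 (139 days) and 408–462 (55 days) also fall in none. The 167-day stretch matters only because it contains month 18.

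SAP 4.10.2 refers to these windows, where applicable, for the primary ORR analysis. The primary ORR is not defined at month 18, so the label does not alter it.

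Finally, a footnote giving the cycle and days might seem enough. It would inform readers of the tables, and the table shells are not among the documents. It would still leave the SAP presenting this row as the protocol's 18-month endpoint.

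**Conclusion.** The point holds. On the nominal schedule, the row labelled Month 18 is the Cycle 17 scan at 16.1 months. Its centre is 57 days (56.9/30.4375 = 1.9 months) before the labelled date, and the window closes 29 days before it. The other three windows contain their labelled dates. The conclusion rests on the stated cycle lengths and survives every month-length convention tried.

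The consequence is a mislabelled secondary result under both response criteria, and a change from the protocol's endpoint that the SAP does not identify. Protocol 9.4.1 reserves hypothesis testing for the primary ORR, so no test is affected, and the stage decisions do not use this row. The size and direction of any effect on the reported rate cannot be worked out from the documents. It should be corrected, but it does not threaten the main conclusions.

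**What to change.** Relabel the row Cycle 17 (about Month 16) in SAP 4.2 and in all outputs, and carry the same label into the endpoint lists in SAP 3.2 and 4.10.3 so that the SAP does not contradict itself. Record in SAP 4.14 that this replaces the protocol's 18-month time point because no scheduled scan falls within 28 days of month 18. Add one sentence stating that the landmark ORR is response status at that scan.

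Optionally, report Cycle 21 (day 603 ± 28, about Month 20) beside it, so that two nearly equidistant scans bracket month 18. If the SAP is not reopened, Protocol 9 allows further modifications to be noted in the clinical study report, and the same statement can go there.

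The cost is a label, a defining sentence, an entry in SAP 4.14 and perhaps one table row. No new scans or data are needed. The sponsor gives up a result labelled 18 months.
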